---

## IV. Data Analysis

### A. Data analysis

To examine the research questions, a repeated measures design will be used. The within-subjects factor will be the time of measurement (pre-survey and 12-month follow-up survey), and the between-subjects factor will be the format of the SSHF curriculum (standard or compressed) and support services.

Descriptive statistics will be computed to summarize the demographic variables and the variables of interest. Shapiro-Wilk tests will be conducted to assess the normality of the data. If the data are not normally distributed, appropriate transformations will be applied, or nonparametric tests will be used. To examine the first research question, a repeated measures analysis of variance (ANOVA) will be conducted with partner relationship attitudes as the dependent variable. The between-subjects factor will be the format of the SSHF curriculum, and the within-subjects factor will be time of measurement. If significant main effects or interactions are found, post hoc tests (e.g., Bonferroni) will be conducted to examine the pairwise comparisons.

The same approach will be used for the remaining research questions, with sexual attitudes, partner relationship behavior, financial attitudes, and employment attitudes as dependent variables. The level of statistical significance will be set at  $p < 0.05$ . Effect sizes will be reported using partial eta-squared ( $\eta^2$ ), which provides an estimate of the proportion of variance in the dependent variable accounted for by each factor in the ANOVA.

To examine the reliability of the scales, Cronbach's alpha will be computed for each construct. A value of 0.70 or higher will indicate acceptable reliability. To examine the validity of the scales, confirmatory factor analysis (CFA) will be conducted to test the hypothesized factor structure of each construct. If the hypothesized factor structure does not fit the data well, exploratory factor analysis (EFA) will be conducted to identify the underlying factor structure. Missing data will be handled using multiple imputation techniques to minimize bias and increase power. Overall, this study will use a repeated measures design with ANOVA to examine the effects of the SSHF curriculum on various domains of relationship and personal functioning and will use reliability and validity analyses to ensure the psychometric properties of the measures.

To measure the impact of dosage in hours on change in pre to post-survey, a regression analysis will be conducted. Specifically, a multiple regression analysis will be conducted with dosage in hours as the predictor variable and change in the dependent variables (partner relationship attitudes, sexual attitudes, partner relationship behavior, financial attitudes, and employment attitudes) as the outcome variables. The model will control for the format of the SSHF curriculum and support services, as well as any demographic variables that are significantly related to the outcome variables.

Assumptions of linear regression, such as normality of residuals, homoscedasticity, and linearity, will be checked using diagnostic plots and statistical tests, such as the Shapiro-Wilk test for normality and the Breusch-Pagan test for homoscedasticity. If the assumptions are violated, appropriate transformations or non-parametric tests will be used. Additionally, the potential for multicollinearity among the predictor variables will be assessed using variance inflation factor (VIF) values. A VIF value greater than 10 indicates problematic multicollinearity, and steps will

be taken to address this issue, such as excluding highly correlated predictor variables. Overall, this study will use regression analysis to examine the relationship between dosage in hours and change in the dependent variables, while controlling for relevant covariates

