Research questions in this study are framed by a descriptive evaluation design to assess whether outcomes improve for at-risk and homeless youth after participating in the AVANCE-Houston Building Futures (A-HBF) Project. Primary outcomes will indicate whether behavior is improving over time for healthy relationships. Secondary benefits will indicate whether the attitudes that facilitate and reflect behavior for healthy family relationships and economic stability (financial and employment) are improving over time. Research questions that focus on primary and secondary outcomes for this study are presented below in Table 2.

Table 2: Outcome Research Questions

No	Research Question	Primary or Secondary Outcome?
R1	Do A-HBF participants report significantly healthier partner relationship attitudes after completing the SSHF curriculum in either a standard (weekly) or compressed (weekend retreat) workshop format and support services?	Secondary Outcome
R2	Do A-HBF participants report significantly healthier sexual attitudes after completing the SSHF curriculum in either a standard (weekly) or compressed (weekend retreat) workshop format and support services?	Secondary Outcome
R3	Do A-HBF participants report significantly healthier partner relationship behavior after completing the SSHF curriculum in either a standard (weekly) or compressed (weekend retreat) workshop format and support services?	Primary Outcome
R4	Do A-HBF participants report significantly healthier financial attitudes after completing the SSHF curriculum in either a standard (weekly) or compressed (weekend retreat) workshop format and support services?	Secondary Outcome
R5	Do A-HBF participants report significantly healthier employment attitudes after completing the SSHF curriculum in either a standard	Secondary Outcome

(weekly) or compressed (weekend retreat) workshop format and support services?

C. Relation to program logic model

Figure 1 in Appendix A presents a logic model to specify a theory of change for delivering A-HBF services. Service delivery processes specified in the model are linked to the desired outcomes for healthy relationships and economic readiness. Model specification incorporates a descriptive study design to conceptualize service delivery and the outcomes assessed for the A-HBF Project.

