Desired Outcomes: Outcomes specified in the logic model theorize the primary and secondary outcomes that are desired for participants after they complete A-HBF services. Secondary outcomes are the improved attitudes that indicate and reflect participant engagement in healthy partner relationship behaviors and capacity for future economic stability. Primary outcomes are the healthier behaviors exhibited by participants for partner relationships that ultimately define the participation benefits for the A-HBF Project. All outcomes specified in the logic model are theorized to be more positive for eligible at-risk and homeless youth after they complete primary services and support services.

D. Hypotheses

Table 3 below presents the hypotheses associated with the primary and secondary research questions for this descriptive study. Primary and secondary outcomes are reported on participant survey measures that are administered shortly after A-HBF enrollment and again one year later after study groups complete services (or should have completed them). Confirmatory hypotheses focus on the extent to which participants report improved attitudes (partner relationship, sexual, financial, and employment) and behaviors (partner relationship) after A-HBF participation.

Table 3: Hypothesized Results

Research Question	Hypothesized Result
R1	Participants will report healthier partner relationship attitudes after they complete primary services and support services in the A-HBF Project.
R2	Participants will report healthier sexual attitudes after they complete primary services and support services in the A-HBF Project.
R3	Participants will report healthier partner relationship behavior after they complete primary services and support services in the A-HBF Project.
R4	Participants will report healthier financial attitudes after they complete primary services and support services in the A-HBF Project.
R5	Participants will report healthier employment attitudes after they complete primary services and support services in the A-HBF Project.

II. Research Design and Staff

A. Research design

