These power analyses assume an Alpha Level of 0.05 with a two-tailed test and power level set at 0.80 (1 – Beta). The estimated effect sizes are all small effects or nearly small effects that would be detected, based on best practices outlined by Cohen (1988) of small effect sizes <0.02 and medium effect sizes <0.15. With these analyses, the proposed research design is demonstrated to measure large, medium, and small changes in participants' responses.

Table 4: Methods to Promote Sufficient Program Participation

What methods will you use to ensure sufficient sample is recruited, enrolls, and participates in the program?	AVANCE will work with schools and their community partners to recruit program participants, and AVANCE will provide incentives for program retention and completion. The CQI process will address issues regarding program recruitment and enrollment to ensure targets are met.
Who will be responsible for recruiting the evaluation sample?	The evaluation sample will not differ from the program population, in that all participants will be invited to participate in the evaluation. Enrollment into the evaluation will be conducted by the CQI Data Manager who will conduct the informed consent process and proctor the baseline data collection efforts.

Please describe any incentives to be offered for program participation and/or completion and/or data collection and/or participation in the evaluation.

Program Participation – AVANCE will provide a series of incentives for program retention (promotional items) and completion (\$75 gift card).

Evaluation Participation – No incentives will be used for the first two data collections- baseline and post-test, while participants are beginning or still engaged in services. A \$50 incentive will be used for the 1-year follow-up survey and will be provided in the form of a Walmart gift card.

D. Lead staff

See Appendix B for CVs of lead evaluation staff.

Table 5: Lead Evaluation Staff

Name	Organization	Role in the Evaluation
[name]	Midwest Evaluation and Research	Principal Investigator
[name]	Midwest Evaluation and Research	Lead Evaluation Consultant
[name], MA	Midwest Evaluation and Research	Evaluation Project Manager
[name]	Midwest Evaluation and Research	CQI Data Manager

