### Model Specification to Predict Outcomes With Dosage

Construct by Outcome	Dependent Variables (follow-up)	Response Codes for Dependent Variables	Dependent Variable Type	Independent Variables
Primary outcome:				
Partner Relationship Behavior: 6 scaled items	DISAG_BE_FU	1 = none of the time to 5 = all of the time	Continuous	Dosage of curriculum; co-variates (using pre-survey scores)
5 scaled items	REL_BE_FU	1 = I am extremely good at this to 4 = I am extremely bad at this		
Secondary outcomes:				
Partner Relationship Attitudes: 9 scaled items	PARTREL_ATT_FU	1 = strongly agree to 4 = strongly disagree	Continuous	Dosage of curriculum; co-variates (using pre-survey scores)
3 scaled items	PARTREL_FUT_ATT_FU	1 = almost no chance to 5 = almost certain		
Sexual Attitudes: 7 scaled items	SEX_ATT_FU	1 = strongly agree to 4 = strongly disagree		
Financial Attitudes: 4 scaled items	FIN_ATT_FU	1 = strongly disagree to 7 = strongly agree		
Employment Attitudes 4 scaled items	EMP_ATT_FU	1 = strongly disagree to 7 = strongly agree		

Step 4 – run the linear regression model: Procedures to run the linear regression model are influenced by dependent variable types. Standard regression is necessary to model the influence of curriculum dosage on continuous dependent variables, such as when participants respond to

---

multiple items in a scaled construct by indicating levels of agreement with statements about key partner relationship attitudes.

Step 5 – interpret model results: Model results demonstrate the benefits of A-HBF participation whenever dosage variables predict more positive primary and secondary outcomes for a construct. For primary outcomes, benefits of receiving *SSHf* curriculum confirm hypotheses when respondents with higher levels of participation more frequently report ( $p < .05$ ):

1. Healthy partner relationship behavior

For secondary outcomes, benefits of receiving *SSHf* curriculum confirm hypotheses when respondents with higher levels of participation more frequently report ( $p < .05$ ):

2. More positive attitudes about partner relationships
3. More positive attitudes about sexual relationships
4. More positive attitudes about financial readiness
5. More positive attitudes about job readiness

---

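### Five hypotheses called confirmatory, measured on seven scales, can each be confirmed at unadjusted p < 0.05; if every null is true, the chance of at least one false confirmed benefit in the dosage regressions is about 9–16%, against 2.5% for a single two-tailed test

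*SAP*

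**What the plan says.** **Status of the hypotheses.** Protocol I.D states: "Confirmatory hypotheses focus on the extent to which participants report improved attitudes". The sentence goes on to list the four attitude domains and partner relationship behavior, so it covers R1 to R5. Table 2 in Protocol I.B makes R3 (behavior) primary and the other four secondary. The text above that table adds: "Primary outcomes will indicate whether behavior is improving over time for healthy relationships".

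**Threshold.** SAP IV.A describes a repeated-measures ANOVA for R1, then says: "The same approach will be used for the remaining research questions". It continues: "The level of statistical significance will be set at" p < 0.05. Bonferroni appears only as an example for post hoc pairwise comparisons after a significant ANOVA effect.

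**Scales.** The SAP table on dosage models has seven dependent variables. R3 has two ("Partner Relationship Behavior: 6 scaled items" and a separate five-item scale). R1 has two ("Partner Relationship Attitudes: 9 scaled items" and a separate three-item scale). R2, R4 and R5 have one each.

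**Decision rule.** Under Step 5, results "confirm hypotheses when respondents with higher levels of participation more frequently report" the healthier behavior or the more positive attitude, at p < .05. The same wording serves the primary and the secondaries, and only favourable results count.

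**Sidedness.** The SAP does not state it. The power section in Protocol II.C does: "These power analyses assume an Alpha Level of 0.05 with a two-tailed test and power level set at 0.80".

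**The concern.** Naming one primary outcome normally limits how many ways a study can claim success. Here it does not. A secondary hypothesis can be confirmed after R3 fails, because Step 5 treats the two tiers alike. R3 itself rests on two scales, and no rule says whether one significant scale is enough. Each hypothesis can also be examined by the ANOVA and by the dosage regression, and neither is named as decisive.

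At stake is the wording of the final report. It could present one or more confirmed benefits that arose by chance, with nothing to tell the reader how many opportunities there were.

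**Working it through.** **1. The plan's own figures.** The documents state no family-wise error rate, so there is none to reproduce. The only calculated figures are the minimum detectable effects in Protocol II.C: 0.017 at N = 1105 and 0.023 at N = 774, with two-tailed alpha 0.05 and power 0.80. I solved the overall F test of a linear regression for f², with noncentrality f² × N. The number of predictors is not given. Fourteen predictors give 0.0168 at N = 1105; twelve or thirteen give 0.0227 or 0.0234 at N = 774. No single number matches both to three decimals. This does not affect the error-rate calculation, and these values are not on the same scale as the mean changes in step 6.

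**2. Inputs.** Alpha is 0.05 per test (SAP IV.A, Step 5), two-tailed (Protocol II.C). A favourable false positive therefore has probability 0.05/2 = 0.025. The number of tests is k = 7 scales (SAP table) or k = 5 constructs (Step 5). The documents give no correlation between test statistics; I assume 0 to 0.7, equal for all pairs. Every null is taken as true.

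**3. Independent tests.**
- Favourable direction: 1 − 0.975^5 = 11.9%; 1 − 0.975^7 = 16.2%.
- Either direction: 1 − 0.95^5 = 22.6%; 1 − 0.95^7 = 30.2%.

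**4. Correlated tests** (equicorrelated normal statistics, one million draws; the zero-correlation row is from the formulas in step 3):

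| Correlation | Benefit, k = 5 | Benefit, k = 7 | Either direction, k = 5 | Either direction, k = 7 |
|---|---|---|---|---|
| 0 | 11.9% | 16.2% | 22.6% | 30.2% |
| 0.3 | 10.5% | 13.7% | 20.9% | 27.1% |
| 0.5 | 9.2% | 11.5% | 18.3% | 22.9% |
| 0.7 | 7.4% | 8.9% | 14.8% | 17.7% |

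**5. The two-scale constructs.** If either scale suffices for R3, its own false-benefit rate is 1 − 0.975² = 4.9% when the scales are independent, about double 2.5%. If instead R1 and R3 each needed both scales, the rate over all five hypotheses would be 1 − 0.975³ × (1 − 0.025²)² = 7.4%, again under independence.

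**6. Cost of control.** The detectable standardised mean change at 80% power is (z + 0.842)/√774, with √774 = 27.82.
- Unadjusted: (1.960 + 0.842)/27.82 = 0.101.
- Strictest Holm step, five tests (0.05/5 = 0.010): (2.576 + 0.842)/27.82 = 0.123.
- Strictest Holm step, seven tests (0.05/7 = 0.0071): (2.690 + 0.842)/27.82 = 0.127.

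With every null true, any false confirmation under Holm must pass that strictest step. The favourable rate is then 1 − (1 − 0.005)^5 = 2.5% for five independent tests, the same as for one test.

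**The case against.** The strongest reply is that the study calls itself descriptive, separates one primary from four secondaries, and never promises a 5% family-wise rate. Many statisticians would not require alpha control over labelled secondary outcomes in a single-group evaluation. That argument has force. It would be enough if the documents did not also call all five hypotheses confirmatory and let each be confirmed on its own p-value. Removing those words for the secondaries would answer most of the concern, and it is one of the options below.

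Two stronger readings are tempting, and the documents support neither.
- *A reader might infer that 18–30% is the chance of a false confirmed benefit.* That is the either-direction rate over seven scales and includes unfavourable results. Step 5 confirms only favourable ones. Rates near that level for benefit would need one-sided tests at 0.05 (about 20–30% over seven scales at correlation 0.5 to 0), and the protocol says two-tailed.
- *A reader might count fourteen tests, ANOVA plus dosage on seven scales, and arrive at 1 − 0.95^14 = 51%.* SAP IV.A names five constructs for the ANOVA, not seven scales. The 51% also counts both directions, and it treats two analyses of the same participants and constructs as independent. The second route adds opportunities, but the documents do not allow a firm figure for it.

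It is also true that chance is not the only threat. In an uncontrolled before-and-after comparison, maturation or selective response can produce apparent improvement that no multiplicity adjustment removes.

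**Conclusion.** The concern holds as a gap in the decision rule. Five hypotheses labelled confirmatory can each be confirmed at unadjusted p < 0.05, and the text reviewed has no error control across outcomes. The false-benefit rate in the dosage regressions is about 9–16% if any of the seven scales can confirm, or 7–12% if there is one test per construct, against 2.5% for one two-tailed test. That is roughly three to six and a half times the single-test rate.

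These figures assume that every null is true, that testing is two-tailed, and that correlations lie between 0 and 0.7. They do not count the ANOVA route. Step 5 gives five verdicts and no rule for combining two scales, so whether five or seven applies is itself undetermined. The SAP text available starts its numbered steps at Step 4, so a provision in Steps 1 to 3 cannot be ruled out, although the decision rule in Step 5 shows none. The repair is a cheap improvement and does not affect data collection.

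**What to change.** 1. Name one analysis, the repeated-measures ANOVA or the dosage regression, as the one that decides each hypothesis. Report the other as descriptive.
2. Define one score per construct. Where two scales are kept, adjust across both. This must include R3: testing R3 at 0.05 without a rule for its two scales leaves the primary claim uncontrolled.
3. Choose one of two courses. Either keep R3 as the only confirmatory hypothesis and remove the confirmatory wording for R1, R2, R4 and R5 in Protocol I.D and SAP Step 5; or apply Holm across all hypotheses that stay confirmatory.

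**Cost.** All of this is wording. With Holm, the detectable mean change at the strictest step rises from 0.101 to 0.123 (five tests) or 0.127 (seven). With relabelling, the secondaries support only exploratory statements. If the sponsor instead gates the secondaries on R3, none of them can be confirmed when R3 fails; at 80% power each and independence, the chance of confirming R3 and a given secondary is 0.8 × 0.8 = 64%, before any further adjustment.

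**Two cautions on these costs.** They are for a mean change, not a dosage slope, for which the documents give no dosage distribution. They also assume 774 one-year responses on every scale. Protocol Table 6 takes R1 to R3 from the nFORM survey, while Table 8 lists only the OLLE survey at one year. Confirm that those items are collected at that wave before R3 is made a gate for a one-year analysis.

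### The dosage regression keeps a demographic only if it is significantly related to the outcomes; this can leave residual confounding in the hours slope, usually small, and a fixed covariate set removes it at almost no cost

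*SAP*

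**What the plan says.** SAP IV.A (Data analysis) describes the dosage analysis this way: "a multiple regression analysis will be conducted with dosage in hours as the predictor variable and change in the dependent variables", for each of the five constructs, from pre- to post-survey. Format and support services are always in the model. Demographics enter conditionally: "as well as any demographic variables that are significantly related to the outcome variables". The section states its aim as to "examine the relationship between dosage in hours and change in the dependent variables, while controlling for relevant covariates". It gives no list of candidate demographics, no significance level for the screen, and no provision to keep a demographic because it is related to hours.

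The SAP table headed Model Specification to Predict Outcomes With Dosage sets out a dosage model with follow-up scores as dependent variables. Its independent variables are dosage and "co-variates (using pre-survey scores", with no demographics named. Step 5 below the table gives the decision rule: "Model results demonstrate the benefits of A-HBF participation whenever dosage variables predict more positive primary and secondary outcomes for a construct", at p < .05.

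Protocol II.A calls the study descriptive. No one is allocated to a number of hours.

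**The concern.** Confounding of the hours slope needs a variable related both to hours and to the outcome. The rule tests only the second link, and does so by statistical significance in the study's own data. A demographic with a weak link to the outcome will often miss the threshold by chance even when it is clearly related to hours. Its share of the association then stays in the hours coefficient, and the final test treats the surviving covariates as though they had been chosen in advance.

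Once format is adjusted for, hours depend largely on attendance. In the text available, covariate adjustment is the only protection against demographic confounding of this slope, and no sensitivity analysis with a fixed set appears. At stake is whether a significant hours coefficient can be read as the SAP wants to read it, as evidence of benefit.

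**Working it through.** **Inputs from the documents.** The expected responses are 1105 at post-test and 774 at follow-up (Protocol II.C, power analysis). The tests are two-sided at 0.05 (Protocol II.C; SAP IV.A: "The level of statistical significance will be set at" p < 0.05). The SAP gives no level for the screen, so 0.05 is assumed there too. The plan states no figure for this point. Its minimum detectable effect sizes cannot be derived without the number of predictors, and they do not bear on the question.

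**Assumptions, because the documents give no correlations.** There are K independent demographics, each correlated r with hours and b = 0.05 with change. Variables are standardised and the true hours effect is zero. Each demographic is screened by its simple correlation with the one outcome being analysed. Format, support services and the pre-survey score are left out for simplicity.

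**Step 1: how often a weak confounder is dropped.** P(drop) ≈ Φ(1.96 − b√N) − Φ(−1.96 − b√N).
- N=1105: b√N = 0.05 × 33.24 = 1.662, so P(drop) ≈ Φ(0.298) = 0.617, about 62%.
- N=774: b√N = 0.05 × 27.82 = 1.391, so P(drop) ≈ Φ(0.569) = 0.715, about 71%.

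**Step 2: what stays in the slope** (K=5, r=0.2, N=1105, all biases in the same direction).
- A dropped demographic tends to have a low sample correlation. Its mean is 0.05 − 0.0301 × 0.3816/0.617 = 0.0314, where 0.0301 = 1/√1105 and 0.3816 is the normal density at 0.298.
- Residual slope ≈ K·r·P(drop)·0.0314 / (1 − K·r²·P(keep)) = 5 × 0.2 × 0.617 × 0.0314 / (1 − 5 × 0.04 × 0.383) = 0.0194/0.923 = 0.021.
- Standard error ≈ 1/√(1105 × 0.923) = 0.0313, so the shift is 0.67 standard errors.
- Rejection ≈ Φ(−1.96 + 0.67) + Φ(−1.96 − 0.67) = 0.099 + 0.004 = 10.3%.

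Simulation of the full two-step procedure agrees. The mean slope is 0.020 with the screen, 0.000 with all five demographics forced in and 0.049 with none. Rejection is 10.1%, 5.3% and 36.3% respectively.

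**Step 3: range of assumptions** (simulated two-sided rejection, true hours effect zero, b = 0.05).

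| Scenario | Hours variance explained (K·r²) | N=1105 | N=774 |
|---|---|---|---|
| One confounder, r=0.2 | 4% | 5.2% | 5.1% |
| Five, r=0.1, aligned | 5% | 6.4% | 6.1% |
| Three, r=0.2, aligned | 12% | 6.6% | 6.5% |
| Four, r=0.2, mixed signs | 16% | 4.8% | 4.7% |
| Five, r=0.3, mixed signs | 45% | 5.0% | 4.6% |
| Five, r=0.3, aligned, one common set kept if related to any of five outcomes | 45% | 6.7% | 6.2% |
| Three, r=0.3, aligned | 27% | 8.7% | 8.5% |
| Five, r=0.2, aligned | 20% | 9.9% | 9.8% |
| Five, r=0.3, aligned | 45% | 17.1% | 16.6% |

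A separate run of the last row gave 17.8% and 17.7%. With every demographic forced in, rejection is about 4-6% throughout. The common-set row also assumes outcomes correlated 0.3 with one another.

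**Step 4: direction.** Step 5 of the SAP counts only results in the benefit direction, where the nominal rate is 2.5%. With five confounders at r=0.2 and N=1105, that rate is 9.5% if all biases favour benefit. If all point against benefit, it falls to between 0.4% and 0.9% for three to five confounders.

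**The case against.** The strongest reply is that material inflation needs an unlikely configuration. Five independent demographics at r=0.3 explain 5 × 0.09 = 45% of the variance in hours. Protocol III.A says post-test data come only from programme completers present at the session, and format, which sets the hours offered, is already in the model. Completers within a format may differ little in hours. The biases must also align; with mixed signs the inflation disappears. This stands, and it limits the size of the point.

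The screening rule can also be read another way. It refers to outcome variables in the plural, so it may mean one common set containing any demographic related to any outcome. On that reading even the extreme scenario falls to about 6-7%, and slopes would not be adjusted differently across outcomes. The text permits either reading.

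Thirdly, a reader might infer that the screened model is the one Step 5 uses to confirm hypotheses. The documents do not establish this. The screen belongs to the pre-to-post change model, while the p<.05 rule sits with a follow-up-score model that lists pre-survey covariates and no screen. SAP IV.A also assigns the research questions to repeated-measures ANOVA. The text available starts at Step 4, so a covariate list may exist in parts not seen; its absence is not held against the plan. The stated screen would still select from such a list by p-value.

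Finally, screening is far better than no adjustment (10.1% against 36.3% in Step 2). What remains is incomplete control: the written rule does not deliver the adjustment for relevant covariates that the same section promises.

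**Conclusion.** The point holds as a cheap improvement. The screen is a stated rule, and it can drop weak confounders of a non-randomised exposure. On the assumptions above, rejection under no hours effect is about 5-7% in most scenarios, about 8-10% with three to five aligned confounders at moderate correlations, and about 17-18% only in the extreme aligned case under outcome-by-outcome screening.

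A reader might infer that the plan's confirmatory test has an error rate three times nominal. The documents do not support that: they give no correlations, they allow a common-set reading, and they do not clearly tie the screened model to the confirmation rule. Nor does the SAP claim that a non-significant demographic has been shown not to confound; it simply leaves it out.

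**What to change.** In SAP IV.A, replace the significance screen with one baseline covariate set fixed before outcome data are seen. It could comprise relationship status and life status, which Protocol I.A names as characteristics of interest, and the demographics collected at baseline, such as age and grade (these two appear in Protocol II.C as eligibility criteria). Keep the whole set in the hours model for every outcome whatever its p-value, alongside format, support services and the pre-survey score.

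Apply the same set to the model in the specification table, and reconcile the two specifications: pre-to-post change in one, follow-up score in the other. State which of them the Step 5 rule uses.

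The cost is SAP wording and a few degrees of freedom out of about 774 to 1105. The change does not remove unmeasured confounding such as motivation to attend, so the interpretation of the hours slope should still say so.
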